3.3 Rationale

There is increasing recognition of the role of the endocannabinoid system in neurobiological processes and behavioral domains relevant to the pathophysiology and treatment of addiction. The phytocannabinoid cannabidiol has attracted considerable attention due to its lack of intoxicating effects, low abuse potential, excellent safety, and unique pharmacological profile.

CBD reliably reduces anxiety-like behavior in animals, attenuates anxiogenic effects of stressful stimuli in healthy and anxious individuals, and disrupts consolidation and facilitates extinction of fear memories. More directly relevant to addiction, CBD prevents reconsolidation of contextual drug-related memories and may decrease impulsive behaviors, craving, and withdrawal. Very recently, rodent studies have provided strong direct evidence of clinically relevant effects of CBD in models of alcohol use disorder (AUD). In two independent studies, treatment with CBD produced marked and persisting decreases in alcohol self-administration and preference for alcohol, and alcohol-, cue- and stress-induced reinstatement. These findings suggest that CBD could have potential as a treatment for AUD. However, there are few studies of the effects of CBD in humans with addictive disorders, and limited data on CBD's safety in AUD populations, particularly at doses shown to be effective in animal models of AUD.

The proposed study is a double-blind, randomized proof-of-concept study designed to assess feasibility and contrast effects of CBD treatment to those of placebo on drinking-related outcomes in patients with alcohol use disorder (AUD). We will evaluate the safety of an extended daily CBD treatment regimen in an AUD population, assess the impact of CBD on neuropsychological and neurophysiological domains implicated in AUD, and

CONFIDENTIAL

This material is the property of the NYU School of Medicine and Langone Health
Do not disclose or use except as authorized in writing by the study sponsor

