21.2 Statistical Hypotheses

Hypothesis 1a: Within-group circulating CBD levels will stabilize within one week, i.e. pre-CBD dosing (12 hour) levels obtained after 1 week of treatment will not differ from those obtained after 4 weeks of treatment at each dose.

Hypothesis 1b: Circulating CBD levels obtained at the 1200 mg/day dose will be comparable to those associated with anti-additive effects in animal models, i.e., in the range of 200-400 ng/ml.

Hypothesis 1c: No clinically significant cognitive or motoric impairments, CBD-related serious adverse events, or persisting adverse effects will be observed.

Hypothesis 2a: Relative to placebo, CBD will improve self-report measures of craving, anxiety, mood, and self-efficacy.

Hypothesis 2b: Relative to placebo, CBD will be associated with decreased stress- and alcohol cue-induced craving and physiological stress response

Hypothesis E: Relative to the placebo-treated group, CBD-treated participants will have fewer heavy drinking days during and for four weeks after treatment with 1200mg/day CBD vs. placebo.

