21.3 Description of Statistical Methods

21.3.1 General Approach

The distributional characteristics of the measures used to investigate the aims of the study will be assessed and data transformations will be explored if necessary. For all hypotheses, linear mixed effects models will be constructed including treatment group as a fixed between-subjects factor, time (T0-T9) as a fixed within-subjects factor, and subject as a random effect. Treatment groups will also be compared on baseline measures of alcohol consumption (% drinking days and % heavy drinking days), alcohol craving (PACS), anxiety (BAI), mood (BDI-II), and self-efficacy (AASE), and baseline scores on these measures will be utilized as covariates for hypothesis evaluation.

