21.3.2 Analysis of the Primary Endpoint(s)

For Hypothesis 1a, acute circulating levels of CBD will be assessed in CBD-treated participants 45 minutes after initial administration (T1, T4), and 45 minutes after administration of the morning dose of medication following 1 day (T2, T5), 1 week (T3, T6), and 4 weeks (T4, T7) of treatment with each dose of CBD. Additionally, circulating levels of CBD will be assessed in CBD-treated participants 12 hours after ingestion of the preceding evening dose following 1 week (T3, T6) and 4 weeks (T4, T7) of administration of each dose of CBD. Levels of CBD (mean and standard deviation) will be reported at each timepoint and effects of dose and timepoint will be evaluated. For Hypothesis 1b, circulating CBD levels (mean and standard deviation) 45 minutes after administration of the morning dose of medication following 1 week (T3, T6) and 4 weeks (T4, T7) of treatment with each dose of CBD will be reported in CBD-treated participants. For Hypothesis 1c, between-group differences on psychomotor tasks (T1-T8), cognitive measures (T3, T6) and number of adverse events (T1-T9) will be assessed.

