21.3.3 Analysis of the Secondary Endpoint(s)

For Hypothesis 2a, between- and within- group differences on measures of craving, anxiety, depression, and self-efficacy (T1, T3, T4, T6, T7, T8) will be evaluated. For Hypothesis 2b, linear mixed effects models will be constructed as described by [name] et al. [123] with treatment group (CBD vs. placebo) included as a fixed

CONFIDENTIAL

This material is the property of the NYU School of Medicine and Langone Health
Do not disclose or use except as authorized in writing by the study sponsor

between-subjects factor, time (nested factor including pre-imagery, imagery, and recovery periods at both T3 and T6) and script type (stress, alcohol cue, neutral) as fixed within-subjects factors, with subject as a random effect. Between- and within- group comparisons and interactions for measures of craving, anxiety, and physiological stress response will be assessed.

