21.3.4 Safety Analyses

Means and standard deviations of acute circulating CBD and THC levels within CBD-treated participants 45 minutes after initial administration (T1, T4), and 45 minutes after administration of the morning dose of medication following 1 day (T2, T5), 1 week (T3, T6), and 4 weeks (T4, T7) of treatment with each dose of CBD will be assessed to determine whether target circulating levels of CBD have been achieved, and whether metabolic transformation of CBD to THC has occurred.

Means and standard deviations of change in 12 hour circulating CBD levels from 1 week to 4 weeks of treatment (T3 to T4, and T6 to T7) within CBD-treated participants will be presented to determine whether extended treatment with CBD results in accumulation of CBD.

The number of participants within each treatment group that were able to pass a battery of psychomotor field sobriety tasks (walk-and-turn task, one-leg stand, Romberg's test, finger-finger test, and counting backwards [97]) within 2 hours of the initial administration of each dose of CBD vs. placebo (T1 and T4) will be analyzed as summary statistics during treatment.

AEs and SAEs, when present, will be collected on an AE Case Report Form at study visits. The form will include an assessment of clinical significance and study relatedness. Serious Adverse Events (SAEs) will be documented on an additional SAE form. These CRFs will be based on those used in recent NIDA Clinical Trials Network trials. To further assess abuse potential, visual analog scales will be used to assess abuse potential. Scales will include desire to use the study medication again, desire to use the study medication again for pleasurable intoxication ("to get high"), and craving for the study medication.

The study may be stopped if there are untoward and concerning levels of Adverse Event (AE) or Serious Adverse Event (SAE) outcomes attributable to CBD or study participation. If the DSMB finds it is likely that CBD is contributing to negative outcomes, they will consider solutions including protocol changes or potentially stopping the study.

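### Hypothesis 1c names no per-dose psychomotor or cognitive contrast; read literally, its model pools 600 mg/day with 1200 mg/day and can dilute an impairment confined to the higher dose

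*Combined protocol and SAP*

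**What the plan says.** Section 21.2 states Hypothesis 1c as "No clinically significant cognitive or motoric impairments, CBD-related serious adverse events, or persisting adverse effects will be observed". It names no dose and gives no margin for clinical significance.

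Section 21.3.2 gives the analysis of 1c in one clause: "between-group differences on psychomotor tasks (T1-T8), cognitive measures (T3, T6) and number of adverse events (T1-T9) will be assessed". Section 21.3.1 supplies the model, a linear mixed model for all hypotheses "including treatment group as a fixed between-subjects factor, time (T0-T9) as a fixed within-subjects factor, and subject as a random effect". Neither section names a group-by-time term, a dose factor or a per-dose contrast for 1c.

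Such effects are named for other hypotheses. For 1a, CBD levels are to be "reported at each timepoint and effects of dose and timepoint will be evaluated". For 2b, section 21.3.3 says "Between- and within- group comparisons and interactions for measures of craving, anxiety, and physiological stress response will be assessed".

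One dose-specific safety display exists. Under section 21.3.4, the number in each group who pass the field sobriety battery "within 2 hours of the initial administration of each dose of CBD vs. placebo (T1 and T4) will be analyzed as summary statistics during treatment".

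Dosing is 600 mg/day in weeks 1-4 and 1200 mg/day in weeks 5-8 (section 7.1.7). T3 is week 1 and T6 is week 5. T8 is week 9, one week after treatment ends (sections 3.3 and 8.3.3).

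**The concern.** The rationale in section 3.3 describes "limited data on CBD's safety in AUD populations, particularly at doses shown to be effective in animal models of AUD", and section 4.1 ties the exposure range seen in animals to 1200 mg/day. The higher dose is therefore where the safety question matters most.

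In a model with group and time as main effects, the only between-group parameter is the group coefficient, which is a difference averaged over visits. For cognition it averages one visit at each dose. For psychomotor tasks it averages both dose periods and an off-drug visit. If CBD impairs function only at 1200 mg/day, the quantity tested is a fraction of the true effect.

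Hypothesis 1c predicts no difference, so lost sensitivity favours the prediction. A null pooled result could be reported as support for 1c although the higher dose had not been examined on its own.

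**Working it through.** **The plan's own figure.** Section 21.4 says that 1c is powered at 0.95, with 40 participants in two groups and alpha 0.05, to detect d of about 0.2. This does not reproduce as a between-group difference. With 20 per arm, two-sided 5% and one measurement, the noncentral t (38 df) gives a detectable d of 1.17. Power at d = 0.2 is 9%, and d = 0.2 would need about 650 per arm. Averaging visits at correlation 0.5 lowers the detectable d only to 1.01 (2 visits) or 0.88 (8 visits). A value near 0.2 appears as Cohen's f, not d, in a group-by-time interaction test at correlation 0.5 (f = 0.19 for 8 visits). The stated figure therefore does not settle which test is meant for 1c.

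**Inputs for the pooling check.** From the documents: 40 randomised 1:1, so n = 20 per arm; alpha 0.05; visits T3 and T6 for cognition and T1-T8 for psychomotor tasks. Assumed: two-sided test, within-person correlation r = 0.5 to 0.7, equal correlation between all visits, equal visit weights, no dropout, effects in SD units of a continuous score.

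**Formulas.** The mean of k visits has variance V = (1 + (k-1)r)/k in SD² units. The standard error of the group difference is SE = sqrt(2V/20). The noncentrality is effect/SE on 38 df.

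**Cognition, 0.8 SD at T6.**
- T6 alone: V = 1, SE = 0.316, noncentrality 0.8/0.316 = 2.53, power 69%.
- Pooled T3 and T6: V = 0.75 at r = 0.5 (SE 0.274) and 0.85 at r = 0.7 (SE 0.292).

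| Effect at 600 mg/day | Pooled effect | Noncentrality (r = 0.5; 0.7) | Pooled power (r = 0.5; 0.7) | T6 alone |
|---|---|---|---|---|
| 0 | (0 + 0.8)/2 = 0.4 | 1.46; 1.37 | 30%; 27% | 69% |
| 0.4 | (0.4 + 0.8)/2 = 0.6 | 2.19; 2.06 | 57%; 52% | 69% |
| 0.8 | (0.8 + 0.8)/2 = 0.8 | 2.92; 2.74 | 81%; 76% | 69% |

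**Psychomotor tasks, 0.8 SD at 1200 mg/day only.** The dilution depends on T4, which section 21.3.2 lists both as the 4-week visit of the first dose and as the initial administration of the second.
- T4 counted as 1200 mg/day: 4 of 8 visits carry the effect, so the pooled effect is 0.8 × 4/8 = 0.4. Power is 38% (r = 0.5) to 30% (r = 0.7), against 88% to 80% for the mean of T4-T7.
- T4 counted as 600 mg/day: 3 of 8 visits carry it, so the pooled effect is 0.8 × 3/8 = 0.3. Power is 23% to 19%, against 86% to 79% for the mean of T5-T7.

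These psychomotor figures are indicative only, because section 21.3.4 describes the field sobriety outcome as a pass count.

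**The case against.** A reader might infer that the plan commits 1c to a single group effect averaged over doses. The documents do not say so. The visit lists in section 21.3.2 can be read as comparisons at each visit. A list of factors does not exclude interactions: section 21.3.3 lists factors for 2b in the same style and then says that interactions will be assessed. Section 21.1 defers a formal SAP to before database lock and unblinding, so the contrasts can still be fixed there. This objection stands: the analysis is unspecified, not explicitly pooled. It does not remove the problem, because no contrast and no rule for combining visits is given, and the only between-group term named is the group effect.

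Section 21.3.4 does look at psychomotor function by dose. That display counts, but it is descriptive and covers only the hours after the first administration of each dose. It covers neither cognition nor continued dosing at 1200 mg/day.

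A reader might also infer that pooling generally costs 40 to 50 points of power. That holds only if 600 mg/day has no effect at all. In the cognitive example the loss is 12-17 points if 600 mg/day has half the effect, and pooling gains 7-12 points if the effects are equal.

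Finally, no margin is stated, so a non-significant difference would not show absence of impairment under either analysis. That is true and is a separate weakness. Per-dose intervals at least show what each dose period excludes, which a pooled interval cannot.

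**Conclusion.** The point holds as a gap in specification. The only between-group term named for 1c is a treatment-group effect. Taken literally it halves a cognitive impairment confined to 1200 mg/day, and reduces a psychomotor one to 37.5-50% depending on how T4 is classed.

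For a 0.8 SD cognitive effect at T6, the cost of pooling runs from about 40 points of power (no effect at 600 mg/day), through 12-17 points (half the effect), to a gain of 7-12 points (equal effects). These figures rest on 20 per arm, a two-sided 5% test, correlation 0.5-0.7, equal visit weights and no dropout. Section 7.1.9 limits the primary analyses to participants who complete treatment through T7, so fewer than 20 per arm may be analysed and all the powers would fall.

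The documents do not support saying that the trial will rest 1c on a pooled test, or that the largest loss is the expected one. They do support saying that the primary safety comparison is not fixed by dose. It is worth settling before unblinding, so that the choice between pooled and dose-specific contrasts cannot follow the data.

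**What to change.** In section 21.3.2 and the formal SAP, add a group-by-time term to the 1c model and prespecify CBD-minus-placebo contrasts, each with a 95% confidence interval:

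- Cognition: T3 (600 mg/day) and T6 (1200 mg/day) separately.
- Psychomotor tasks: the mean over the 600 mg/day visits and the mean over the 1200 mg/day visits separately, with T8 reported on its own as an off-drug visit.
- T4: state whether the psychomotor tests entering this comparison precede or follow the first 1200 mg/day administration, and assign the visit accordingly. Sections 7.3.1 and 21.3.4 place a field sobriety battery after the on-site dose at T4, but do not say that this is the T4 value used in the T1-T8 comparison.

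Report both dose-period contrasts, with the pooled estimate as an optional addition, and do not claim absence of impairment from the pooled effect alone. Resting 1c on whichever dose period looks worse is not a substitute: without a margin it gives no decision, and picking the worse of two estimates leans towards apparent impairment.

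The cost is SAP wording and one extra model term, with no new data. There are two contrasts instead of one, and less power if the effect is the same at both doses (69% against 76-81% in the cognitive example). At 20 per arm a T6 contrast reaches 95% power only at d of about 1.17, so the sensitivity statement for 1c in section 21.4 should be corrected at the same time.

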21.3.3 Analysis of the Secondary Endpoint(s)

For Hypothesis 2a, between- and within- group differences on measures of craving, anxiety, depression, and self-efficacy (T1, T3, T4, T6, T7, T8) will be evaluated. For Hypothesis 2b, linear mixed effects models will be constructed as described by [name] et al. [123] with treatment group (CBD vs. placebo) included as a fixed

CONFIDENTIAL

This material is the property of the NYU School of Medicine and Langone Health
Do not disclose or use except as authorized in writing by the study sponsor

between-subjects factor, time (nested factor including pre-imagery, imagery, and recovery periods at both T3 and T6) and script type (stress, alcohol cue, neutral) as fixed within-subjects factors, with subject as a random effect. Between- and within- group comparisons and interactions for measures of craving, anxiety, and physiological stress response will be assessed.

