The Cue and Stress Response Task will be performed at the 5- week time-point using methodology developed in [name]'s lab, similar to those in used in past studies with alcohol dependent patients [112, 113]. [name] will provide consultation on the implementation of these methods. Briefly, imagery scripts will be developed at baseline and again following 4 weeks of treatment. Stress imagery scripts will be based on a recent highly stressful situation the participant has experienced unrelated to alcohol use. Alcohol cue scripts will be derived from a recent event that included alcohol-related stimuli and led to alcohol use. Neutral or relaxing scripts will also be developed. All scripts will be developed by obtaining specific details of stimulus and response, including contextual details, cognitive and verbal content, affective experience, and bodily sensations. These details form the basis of a 5-minute imagery script, which will be developed for each of the three conditions. Imagery sessions will be structured with a 5-minute pre-imagery period, a 5-minute imagery period, and a 5-minute recovery period. Pulse, skin conductance, heart rate variability, and blood pressure will be monitored during each imagery session with an ADInstruments PowerLab 4/30 Galvanic Skin Response device and a Contec Patient Monitor. In Human laboratory studies with CBD, skin conductance and amygdala activation were reduced by CBD in a closely correlated manner [59], suggesting threat-related sympathetic arousal may serve as a proxy for amygdala activation [114]. Participants will complete Likert scale ratings of vividness, craving, anxiety, and the 30-item Differential Emotion Scale [112, 113] following each of the three periods. After each condition, a progressive relaxation procedure will be implemented to facilitate return to baseline of vital signs, craving and anxiety, an approximate period of 10 minutes, as shown in previous research from the [name] lab [112, 113]. The entire imagery protocol will take 120 minutes. The order of the sessions will be randomized and counterbalanced among participants. This task will be completed at 5 weeks, i.e. after 1 week of treatment at 1200mg daily. At this point, we expect steady-state circulating CBD levels to have been reached. It is important to assess stress- and cue- response at the high dose because it is possible that anxiolytic effects decrease at high doses of CBD, while effects on alcohol consumption are expected to increase with dose.

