The Cue and Stress Response Task will be performed at the 5- week time-point using methodology developed in [name]'s lab, similar to those in used in past studies with alcohol dependent patients [112, 113]. [name] will provide consultation on the implementation of these methods. Briefly, imagery scripts will be developed at baseline and again following 4 weeks of treatment. Stress imagery scripts will be based on a recent highly stressful situation the participant has experienced unrelated to alcohol use. Alcohol cue scripts will be derived from a recent event that included alcohol-related stimuli and led to alcohol use. Neutral or relaxing scripts will also be developed. All scripts will be developed by obtaining specific details of stimulus and response, including contextual details, cognitive and verbal content, affective experience, and bodily sensations. These details form the basis of a 5-minute imagery script, which will be developed for each of the three conditions. Imagery sessions will be structured with a 5-minute pre-imagery period, a 5-minute imagery period, and a 5-minute recovery period. Pulse, skin conductance, heart rate variability, and blood pressure will be monitored during each imagery session with an ADInstruments PowerLab 4/30 Galvanic Skin Response device and a Contec Patient Monitor. In Human laboratory studies with CBD, skin conductance and amygdala activation were reduced by CBD in a closely correlated manner [59], suggesting threat-related sympathetic arousal may serve as a proxy for amygdala activation [114]. Participants will complete Likert scale ratings of vividness, craving, anxiety, and the 30-item Differential Emotion Scale [112, 113] following each of the three periods. After each condition, a progressive relaxation procedure will be implemented to facilitate return to baseline of vital signs, craving and anxiety, an approximate period of 10 minutes, as shown in previous research from the [name] lab [112, 113]. The entire imagery protocol will take 120 minutes. The order of the sessions will be randomized and counterbalanced among participants. This task will be completed at 5 weeks, i.e. after 1 week of treatment at 1200mg daily. At this point, we expect steady-state circulating CBD levels to have been reached. It is important to assess stress- and cue- response at the high dose because it is possible that anxiolytic effects decrease at high doses of CBD, while effects on alcohol consumption are expected to increase with dose.

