8.3.3 Intermediate Visits

8.3.3.1 Visit 2

1 day (T2)

CONFIDENTIAL

This material is the property of the NYU School of Medicine and Langone Health
Do not disclose or use except as authorized in writing by the study sponsor

- Collect blood for CBD, Delta-9 THC, 11-Hydroxy Delta-9 THC, Delta-9 Carboxy THC and Anandamide levels (45 minutes post-CBD levels)
- Record adverse events as reported by participant or observed by the coordinator
- Record vital signs, results of evaluations of safety, and psychomotor effects

8.3.3.2 Visit 3

1 week (T3)

- Collect urine for urine drug analysis and urine pregnancy test
- Collect blood for CBD, Delta-9 THC, 11-Hydroxy Delta-9 THC, Delta-9 Carboxy THC and Anandamide levels (pre-CBD and 45 minutes post-CBD levels)
- Record adverse events as reported by participant or observed by investigator
- Record vital signs, results of evaluations of safety, psychomotor/subjective effects, cognitive function, AUD-related domains and drinking
- Provide additional medication to the participant according to the study's MOP requirements
- Record participant's adherence to treatment program

8.3.3.3 Visit 4

4 weeks (T4)

- Collect urine for urine drug analysis and urine pregnancy test
- Collect blood for CBD, Delta-9 THC, 11-Hydroxy Delta-9 THC, Delta-9 Carboxy THC and Anandamide levels (pre-CBD and 45 minutes post-CBD levels), LFTs
- Collect blood for CDT levels
- Record adverse events as reported by participant or observed by investigator
- Record vital signs, results of evaluations of safety, psychomotor/subjective effects, AUD-related domains, and drinking
- Provide additional medication to the participant according to the study's MOP requirements
- Record participant's adherence to treatment program

8.3.3.4 Visit 5

4 weeks + 1 day (T5)

- Collect blood for CBD, Delta-9 THC, 11-Hydroxy Delta-9 THC, Delta-9 Carboxy THC and Anandamide levels (45 minutes post-CBD levels)
- Record adverse events as reported by participant or observed by coordinator
- Record vital signs, results of evaluations of safety, psychomotor/subjective effects

8.3.3.5 Visit 6

5 weeks (T6)

- Collect urine for urine drug analysis and urine pregnancy test
- Collect blood for CBD, Delta-9 THC, 11-Hydroxy Delta-9 THC, Delta-9 Carboxy THC and Anandamide levels (pre-CBD and 45 minutes post-CBD levels)
- Record adverse events as reported by participant or observed by investigator.

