- Record vital signs, results of evaluations of safety, psychomotor/subjective effects, cognitive function, AUD-related domains, cue/stress response task, and drinking
- Provide additional medication to the participant according to the study's MOP requirements
- Record participant's adherence to treatment program

8.3.3.6 Visit 7

8 weeks (T7)

- Collect urine for urine drug analysis and urine pregnancy test
- Collect blood for CBD, Delta-9 THC, 11-Hydroxy Delta-9 THC, Delta-9 Carboxy THC and Anandamide levels (pre-CBD and 45 minutes post-CBD levels), LFTs
- Collect blood for CDT levels
- Record adverse events as reported by participant or observed by investigator

CONFIDENTIAL

This material is the property of the NYU School of Medicine and Langone Health
Do not disclose or use except as authorized in writing by the study sponsor

- Record vital signs, results of evaluations of safety, psychomotor/subjective effects, AUD-related domains, and drinking
- Provide additional medication to the participant according to the study's MOP requirements
- Record participant's adherence to treatment program

8.3.3.7 Visit 8

9 weeks (T8)

- Collect urine for urine drug analysis and urine pregnancy test
- Collect blood for CBD, Delta-9 THC, 11-Hydroxy Delta-9 THC, Delta-9 Carboxy THC and Anandamide levels (pre-CBD levels), LFTs
- Record adverse events as reported by participant or observed by coordinator
- Record vital signs, results of evaluations of safety, psychomotor/subjective effects, AUD-related domains, and drinking

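### Hypothesis 2b is modelled at T3 and T6 although the cue/stress task is scheduled only at T6, and Hypothesis 2a uses T1 both as an outcome visit and as the covariate

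*Combined protocol and SAP*

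**What the plan says.** **Hypothesis 2b.** Section 21.3.3 builds a mixed model with treatment group, script type (stress, alcohol cue, neutral) and "time (nested factor including pre-imagery, imagery, and recovery periods at both T3 and T6". The sections that describe the task place it at one visit:

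- Section 5.1.2: "This task will be completed at 5 weeks, i.e. after 1 week of treatment at 1200mg daily".
- Section 8.1: "The Cue and Stress Response Task will be performed at the 5- week time-point".
- Section 8.3.3, T3 list: "psychomotor/subjective effects, cognitive function, AUD-related domains and drinking". The task is not named.
- Section 8.3.3, T6 list: "cognitive function, AUD-related domains, cue/stress response task, and drinking".

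Section 5.1.2 also says that "imagery scripts will be developed at baseline and again following 4 weeks of treatment". Section 21.4 gives d = 0.3 for 2b without saying how many sessions it assumes.

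**Hypothesis 2a.** Section 21.3.3: "between- and within- group differences on measures of craving, anxiety, depression, and self-efficacy (T1, T3, T4, T6, T7, T8) will be evaluated". T1 is the baseline visit (sections 8.3.2 and 21.3.10). Section 21.3.1 describes the model for all hypotheses as including "treatment group as a fixed between-subjects factor, time (T0-T9) as a fixed within-subjects factor, and subject as a random effect", and adds baseline scores on craving, anxiety, mood, self-efficacy and drinking as covariates.

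**Timing of the Beck scales (BAI, BDI-II).** Section 5.1.2 gives three occasions: before treatment, at its end, and at a follow-up two weeks out. Section 8.1 gives before treatment, weeks 1, 4, 5 and 8, and separately the end of treatment.

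**The concern.** A model can estimate a visit effect only if the measurement is taken at more than one visit. If the task is run only at T6, the 2b terms that involve visit have no data behind them, and a reader cannot tell whether the sensitivity quoted in 21.4 belongs to the one-session design in the procedures or to a two-session design.

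For 2a, once T1 has been adjusted for, the T1 rows carry no information on treatment. If they stay in as outcomes and one group coefficient covers all visits, they pull that coefficient towards zero. In a proof-of-concept trial of 40 people, the estimate and its interval are what later planning will use, so an estimate that is too small matters even if the p-value is right.

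**Working it through.** **1. The figure in 21.4.** Inputs: power 0.95, alpha 0.05, 40 participants in 2 groups (1:1, so 20 per arm), d = 0.3 for 2b.

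As a plain two-sided between-group comparison, power at d = 0.3 is 15.2%, and the d detectable with 95% power is 1.17. The figure does not reproduce on that reading.

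Read instead as Cohen's f for a group-by-time interaction over m levels, the noncentrality is f² × N × m / (1 − ρ), with df m − 1 and 38(m − 1). The correlation ρ is not in the documents, so it is assumed over a range. For f = 0.3:

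| Levels m | ρ = 0.3 | ρ = 0.5 | ρ = 0.7 |
|---|---|---|---|
| 2 (for example two visits) | 0.878 | 0.959 | 0.998 |
| 3 (for example three periods at one visit) | 0.941 | 0.988 | 1.000 |

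Two visits at ρ = 0.5 and three periods at ρ = 0.3 both come close to 0.95. The number of sessions behind d = 0.3 therefore cannot be recovered from the figure.

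**2. Cells for 2b.** As modelled: 3 scripts × 3 periods × 2 visits = 18 per participant. As scheduled: 3 × 3 × 1 = 9. With two groups, the full factorial has 2 × 3 × 6 = 36 cell means, and T6 alone supports 2 × 3 × 3 = 18. Degrees of freedom by term:

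| Term | T3 and T6 | T6 only |
|---|---|---|
| Group | 1 | 1 |
| Script | 2 | 2 |
| Group × script | 2 | 2 |
| Time (period within visit) | 5 | 2 |
| Group × time | 5 | 2 |
| Script × time | 10 | 4 |
| Group × script × time | 10 | 4 |

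The terms total 35 df (36 − 1) and 17 df (18 − 1). What is lost is everything that involves visit.

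**3. T1 in 2a.** The outcome visits are T1 plus five later ones (T3, T4, T6, T7, T8). With complete data, the group coefficient of the random-intercept model with baseline covariates equals that from regressing each participant's mean on group and those covariates. The six-visit mean is

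M = (Y_T1 + 5 × P) / 6,

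where P is the mean of the five later visits. Y_T1 is itself a covariate, so its own regression leaves a group coefficient of 0 and a residual of 0. Hence

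coefficient for M = (0 + 5 × coefficient for P) / 6 = 5/6 of the coefficient for P.

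The residuals, and so the standard error, shrink by the same 5/6 as long as the estimated subject variance is above zero. The t statistic is unchanged. Further baseline covariates do not alter the argument.

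Simulation check: 20,000 trials, N = 40, one baseline covariate, assumed constant effect 0.80 SD, ρ = 0.5.

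| | T1 also an outcome | T1 covariate only |
|---|---|---|
| Mean estimate | 0.666 | 0.799 |
| Mean standard error | 0.157 | 0.188 |
| Rejection rate | 0.985 | 0.985 |

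The mean ratio of the estimates was 0.8333 at ρ = 0.3, 0.5 and 0.7.

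**4. Visit lists.** Sections 8.3.2 and 8.3.3 record the AUD-related domains at T1, T3, T4, T6, T7 and T8, and not at T2 or T5. That agrees with 21.3.3. Section 8.1 agrees too if its separate end-of-treatment occasion means T8. Section 5.1.2 does not agree: section 3.3 places the post-treatment assessments 1 and 4 weeks after treatment stops, so nothing falls at two weeks.

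**The case against.** **The group-by-time term is unnamed, not excluded.** Section 21.3.1 says the models include group, time and subject. Looking at between- and within-group differences with T1 in the list is naturally read as a group-by-time analysis. Taken as f = 0.2 over six visits with assumed ρ = 0.5, the 2a figure in 21.4 gives interaction power of 0.936, which fits that reading; at ρ = 0.3 and 0.7 the power is 0.817 and 0.997, so this is an inference only. The objection stands to this extent: the 5/6 result is conditional on fitting the model as written. What remains is that 21.3.3 mentions interactions only after the 2b model, and no 2a contrast is named.

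**A constant effect is a simplification.** T3 and T4 fall in the first dose period, T6 and T7 in the second, and T8 after treatment. That is fair, and it is a further reason for a group-by-visit term.

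**Stronger readings that a reader might infer.**

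- That 2b cannot be analysed. It can: the model fits on T6, and group, script and group by script keep their degrees of freedom.
- That the 2a test is invalid or loses power. It is not and does not: coefficient and standard error shrink together.
- That the documents leave the timing of the task open. Developing scripts twice may be a trace of a two-session design, but 5.1.2 and 8.1 both time the task at 5 weeks and justify this by the wish to assess response at the higher dose. Only 21.3.3 names T3.
- That the Beck scale schedules are in general disarray. Only 5.1.2 clearly departs from the rest.

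**A formal SAP is still to come (21.1).** This makes correction cheap, but an SAP drafted from 21.3.3 would carry both problems forward.

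**Conclusion.** Both parts hold, within limits.

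**2b.** Section 21.3.3 conflicts with 5.1.2, 8.1 and 8.3.3. Half of the modelled cells (9 of 18 per participant) have no scheduled data, and the visit and group-by-visit terms cannot be estimated. The weight of the text supports T6 only. No loss of sensitivity can be calculated, because 21.4 does not give its inputs.

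**2a.** If the model is fitted as written, with complete data and a constant post-baseline effect, the group coefficient and its standard error are each 5/6 of their correct size. The reported effect and its interval would be one sixth too small, while the test and power stay the same. If a group-by-time term is intended, that shrinkage does not follow, but the term and the contrast still have to be stated.

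These are secondary hypotheses. The corrections should be made before unblinding, but they do not threaten the primary objective.

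**What to change.** - **2b:** reconcile 21.3.3 with 5.1.2, 8.1 and 8.3.3. On the present text, specify group × script × period at T6 with a random subject effect. In 21.4, state how many sessions lie behind d = 0.3, and restate the figure if it assumed two. If a T3 session is in fact intended, add it to the procedure sections and the T3 visit list.
- **2a:** use T1 as a covariate only, with T3, T4, T6, T7 and T8 as outcomes, a group-by-visit term and a named covariate-adjusted group contrast. Alternatively, keep T1 as an outcome with group means constrained equal at T1, and drop the baseline covariate.
- **Minor:** bring the Beck scale timing in 5.1.2 into line with 21.3.3 and the visit lists, and say in 8.1 which visit the end of treatment is.

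**Cost.** For T6 only, wording, since 21.1 already promises a formal SAP before database lock and unblinding; the restated 2b sensitivity may be less favourable. A T3 session would add a further imagery protocol, which 5.1.2 puts at 120 minutes, for each participant.
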